5.4.2.3. HBeAg Seroclearance and Seroconversion

Seroclearance of HBeAg is defined as (quantitative) HBeAg <LLOQ. The HBeAg seroclearance will be summarized only for HBeAg positive participants at study entry.

Seroclearance will be analyzed as observed case without imputation and with imputation using LOCF approach. For the imputation with LOCF approach, we impute the missing data with the following restriction. If the HBeAg value at Weeks 40 or 48 is missing, the LOCF approach will be used with the condition that no value more than 8 weeks prior to the respective time point may be carried forward. At FU Weeks, if an HBeAg value is missing, then LOCF approach will be used

with the condition that no value before the FU phase or more than 12 weeks prior to the respective time point will be used. For all other time points, seroclearance will be analyzed as observed case without imputation.

The proportion of participants who achieve HBeAg seroclearance over time will be summarized.

Seroconversion of HBeAg is defined as having achieved HBeAg seroclearance together with appearance of anti-HBe antibodies. Appearance of anti-HBe antibodies is defined as a baseline anti-HBe antibodies (qualitative) with a "NEGATIVE" result and a post-baseline assessment with "POSITIVE" result. The seroconversion of HBeAg will be summarized only for HBeAg positive participants at study entry.

The seroconversion will only be assessed at the time points when the anti-HBe antibodies assessment is available. If the HBeAg value is missing at that specific time point, then the non-missing lab test closest to that specific timepoint will be used. If the non-missing lab test before and after the specific timepoint fall equidistant from the target timepoint, the later one will be used to impute the missing value.

The number and proportion of participants who achieve HBeAg seroconversion will be summarized.

5.4.2.4. HBsAg, HBeAg, HBV DNA and ALT

5.4.2.4.1. Values and Changes Over Time

5.4.2.4.1.1. Change from Baseline Over Time

Descriptive statistics on actual values [original unit and \log_{10} transformed values (except for ALT)] and changes from baseline (in original unit for ALT and \log_{10} transformed values otherwise) over time in HBsAg, HBeAg (for HBeAg positive participants at study entry), HBV DNA and ALT will be summarized and mean (+/- SE) plots of the values and the change from baseline over time will be presented.

Change from baseline based on \log_{10} transform for quantitative HBsAg, HBeAg (for HBeAg positive participants at study entry) and HBV DNA will be analyzed using mixed effects model for repeated measures [MMRM] including analysis time point (week), and HBV baseline status (HBeAg positive and not currently treated or HBeAg negative and virologically suppressed) as fixed effects. In addition, the above model will be augmented with a HBV baseline status by time point interaction term. The covariance structure will include a random intercept at the level of the participant to capture between-participant variability, while within-participant variability will be captured with a Compound Symmetry (type=CS) covariance matrix. In case of convergence problems, another simpler variance-covariance structure such as Toeplitz or AR (1) will be considered. The selection of any of these structures will be determined after exploration of the observed correlation structure. The LS mean of change from baseline, standard error (SE), and 80% CI will be provided.

Spaghetti plots for both absolute values and changes from baseline of HBsAg, HBeAg, HBV DNA, and ALT will be presented over time.

Waterfall plots for changes from baseline of HBsAg, HBeAg, HBV DNA, and ALT will also be presented.

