## Follow-up Procedures and Criteria for Re-initiation of NA Treatment

The follow-up period will be extended for participants who are receiving optional treatment with PegIFN- $\alpha$ 2a and who meet NA treatment completion criteria at the end of treatment with NA and PegIFN- $\alpha$ 2a to ensure all participants have at least one year of follow-up after NA treatment cessation.

To ensure safety of patients during the follow-up phase, an ALT flare management plan is in place, including a high visit frequency for patients after completion of NA treatment (at Week 48), and weekly visits for patients with ALT/AST  $\geq$ 3x upper limit of normal (ULN) and  $\geq$ 3x nadir until stabilization.

Increases in ALT and HBV DNA are frequently seen in patients after discontinuation of NA treatment. These ALT elevations can be reflecting an activation of the host cellular immune response and can as such lead to functional cure. Cases of fulminant HBV reactivation with fatal outcome were described after cessation of NA treatment, but the vast majority of such cases were described in patients with decompensated liver disease at the time of NA discontinuation. These patients are not eligible to participate in the study. Still, a vigilant follow-up of patients during this phase of the study is critical to ensure patient safety. Increases in ALT that are accompanied by signs of decreased liver function, or an HBV DNA value of  $>100,000$  IU/mL (irrespective of confirmation and/or ALT increase), will trigger immediate re-initiation of NA treatment based on protocol-defined NA re-treatment criteria (see Section 6.6.2).

Re-initiation of NA treatment is also required in case of confirmed HBeAg seroconversion (HBeAg positive after it was negative at NA completion), in case of confirmed\* ALT increase ( $>5x$  ULN) in combination with increased HBV DNA replication ( $>2,000$  IU/mL), and in case of confirmed\* increased HBV DNA replication at higher levels ( $>20,000$  IU/mL).

\* At least 4 weeks apart

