#### **5.1. Inclusion Criteria**

Each potential participant must satisfy all of the following criteria to be enrolled in the study:

1. Adult participants  $\geq 18$  years of age (or the legal age of consent in the jurisdiction in which the study is taking place) to  $\leq 65$  years of age.
2. Participants must be medically stable on the basis of physical examination, medical history, vital signs, and triplicate 12-lead ECG performed at screening. Any abnormalities must be consistent with the underlying illness in the study population and this

determination must be recorded in the participant's source documents and initialed by the investigator.

3. Participants must have HBV infection documented by serum HBsAg positivity at screening. In addition, chronicity must be documented by any of the following at least 6 months prior to screening: serum HBsAg positivity, HBeAg positivity or HBV DNA positivity, ALT elevation above ULN without another cause than HBV infection, documented transmission event, liver biopsy with changes consistent with chronic HBV. If none of the above are available, the following ways of documenting chronicity are acceptable at the time of screening: absence of marker for acute infection such as immunoglobulin M (IgM) anti-HBs and anti-HBc antibodies, which can be tested at screening.
4. Participants who are not currently treated (defined as not having been on HBV treatment, including NAs and IFN products within 6 months prior to screening), including treatment-naïve participants (defined as never having received HBV treatment, including NAs and IFN products) should:
  - a. be HBeAg positive, AND
  - b. have serum HBV DNA at screening  $\geq 20,000$  IU /mL, AND
  - c. have ALT levels at screening  $<10$ x ULN, AND
  - d. have indication for NA treatment according to local standard practice.
5. Virologically suppressed participants should:
  - a. be HBeAg negative, AND
  - b. be on stable HBV treatment, defined as currently receiving NA treatment (ETV, tenofovir disoproxil, or TAF) for at least 6 months prior to screening and have been on the same NA treatment regimen (at the same dose) for at least 3 months at the time of screening, AND
  - c. have serum HBV DNA  $<60$  IU/mL on 2 measurements at least 3 months apart (one of which is at screening), AND
  - d. have documented ALT values  $<2.0$ x ULN on 2 measurements at least 3 months apart (one of which is at screening).

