#### Study Intervention Administration

Study intervention administration must be captured in the source documents and the CRF.

JNJ-3989 injections will be administered SC (preferably in the abdomen) at the study site.

In between study visits, participants will take their oral study intervention (NA treatment) at home and they will bring their oral study intervention with them to each study visit. At study visits, the

oral study intervention should be taken on site to allow biochemistry and renal biomarker samples to be taken in fasted conditions.

During the study, virologically suppressed participants will continue the same NA treatment they were receiving at time of screening (and during at least 3 months prior to screening). In case participants experienced toxicity to ETV, tenofovir disoproxil, or TAF prior to screening, they should be treated with one of the other two NAs during this study.

Participants who are not receiving any HBV treatment at screening will receive tenofovir disoproxil at start of intervention.

If clinically indicated, switching from one NA treatment (ETV, tenofovir disoproxil, or TAF) to another NA treatment (ETV, tenofovir disoproxil, or TAF) during the study is allowed for all participants after consultation with the sponsor.

For PegIFN- $\alpha$ 2a, administration should be done SC in the thigh or abdomen, preferably in the evening by self-injection. Used PegIFN- $\alpha$ 2a syringes should be separated from the needle via the sharps container and then placed into their original box and returned to the site, if allowed per local guidelines and regulations. The used needles in the sharps container will be returned to the study site after completion of treatment with PegIFN-  $\alpha$ 2a or disposed of following local standard procedures. If desired, participants can also choose to have the weekly administration of PegIFN- $\alpha$ 2a performed at the study site irrespective of the time of day.

If JNJ-3989 and PegIFN- $\alpha$ 2a are both injected in the abdomen, they should be injected into different areas of the abdomen and approximate location should be recorded.

For a definition of study intervention overdose, refer to Section 8.5.7.

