5.1.5. Data Handling Rules

Those measurements collected from screening visit to the end of study will be handled according to the following rules summarized in [Table 3](#).

Table 3: Data Handling Rules for HBV Virology and Serology Assessments

HBV parameter	LLOQ	ULOQ	Imputed Values	
			If value < LLOQ	If value > ULOQ
HBsAg	0.05 IU/mL	249,750.00 IU/mL with dilution	0.025 IU/mL ^(a)	274,725.00 IU/mL ^(b) with dilution
HBeAg	0.11 IU/mL	7,000.00 IU/mL with dilution	0.055 IU/mL ^(a)	7,700.00 IU/mL ^(b) with dilution
HBcrAg*	3.0 Log ₁₀ U/mL	9.0 Log ₁₀ U/mL with dilution	2.7 Log ₁₀ U/mL	9.9 Log ₁₀ U/mL ^(b) with dilution
HBV DNA	20 IU/mL	170,000,000 IU/mL w/o dilution	If target detected: 15 IU/mL** If target not detected: 5 IU/mL **	187,000,000 ^{(b)(c)} IU/mL w/o dilution
HBV RNA*	LLOQ = 2.939 log ₁₀ cp/mL (i.e., 869 cp/mL) LOD = 1.398 log ₁₀ cp/mL (i.e., 25 cp/mL)	NAP	If < LOD or target not detected then 1.114 log ₁₀ cp/mL (13 cp/mL)	NAP
Anti-HBs	5 mIU/mL	10000.0 mIU/mL	2.5 mIU/mL ^(a)	11000.0 mIU/mL ^(b)

* As new assays become available different data handling rules may apply

** For HBV DNA <LLOQ: Spaghetti plots showing absolute values, the imputed value will be 15 IU/mL for both target detected and target not detected. All other tables, listings and figures, will be produced using 15 IU/mL as an imputed value if target is detected and 5 IU/mL if target is not detected.

Key: NAP=Not applicable

(a) LLOQ/2

(b) ULOQ+(ULOQ/10)

(c) If the original result > ULOQ, then take the re-test value (i.e., diluted result). If the diluted result is not available, use the imputed value of the original result indicated in this table.

All other non-intrahepatic viral activity data not included in the data handling rules above, as well as continuous intrahepatic parameters obtained from liver biopsies (e.g., liver concentration of JNJ-3989), with values <LLOQ will be imputed by the LLOQ divided by 2. For parameters reported on the log scale, imputed values should be derived on the linear scale, not the log scale, and then converted back to the log scale. E.g., if a parameter has LLOQ = 3.0 Log₁₀ U/mL (equivalent to 1,000 U/mL), the imputed value should be log₁₀(10^{LLOQ}/2) = LLOQ - log₁₀(2) = 2.7 Log₁₀ U/mL (equivalent to 500 U/mL).

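### SAP 5.4.2.4.1.1: one common covariance would miscalibrate any status-specific MMRM interval for on-treatment HBV DNA; the random intercept is redundant beside CS, and Toeplitz is not a simpler fallback (minor)

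*SAP*

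**What the plan says.** SAP 5.4.2.4.1.1 models log10 change from baseline in HBsAg, HBeAg (HBeAg-positive participants only) and HBV DNA. The fixed effects are week and HBV baseline status, and a second version adds their interaction. The covariance is described as follows: "The covariance structure will include a random intercept at the level of the participant to capture between-participant variability, while within-participant variability will be captured" by a type=CS matrix. The fallback reads: "In case of convergence problems, another simpler variance-covariance structure such as Toeplitz or AR (1) will be considered". The choice is to follow inspection of the observed correlation; unequal variance is not mentioned. The output is an LS mean with SE and 80% CI. The text does not say whether the LS means are status-specific or averaged over status.

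Four other places bear on the spread of HBV DNA change:

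- Protocol 5.1, criterion 5c (suppressed group): HBV DNA below 60 "IU/mL on 2 measurements at least 3 months apart (one of which is at screening), AND".
- Protocol 5.1, criterion 4b (untreated group): they should "have serum HBV DNA at screening" of at least 20,000 IU/mL.
- Protocol 6.1: "virologically suppressed participants will continue the same NA treatment they were receiving at time of screening", whereas "Participants who are not receiving any HBV treatment at screening will receive tenofovir disoproxil at start of intervention".
- SAP 5.1.5, Table 3, for HBV DNA below the LLOQ of 20 IU/mL: apart from spaghetti plots of absolute values, outputs "will be produced using 15 IU/mL as an imputed value if target is detected and 5 IU/mL if target is not detected".

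**The concern.** A common covariance gives both groups one SD, so at equal group size their intervals have equal width. The entry criteria and the imputation rule confine suppressed participants who stay suppressed to a narrow band. Untreated participants fall by several log10 from widely scattered starting values. Pooling then makes the interval too narrow where change is variable and too wide where it is not. Since the study tests nothing, the 80% interval is its main statement of uncertainty.

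The covariance wording has two faults that do not depend on any SD. It counts the same between-participant component twice, which can itself cause convergence trouble. It then answers such trouble with a list headed by a structure with more parameters than the one it replaces.

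**Working it through.** The documents give no SD, sample-size calculation or power for this model, so there is no stated figure to reproduce. The limits below come from the documents. All SDs are assumed.

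**Limits on change in HBV DNA (log10 IU/mL)**

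- Suppressed, if Day 1 stays below 60: the largest fall is log10(60/5) = 1.08. Someone always below LLOQ changes by 0 or by log10(15/5) = 0.48.
- Untreated, falling from 20,000 IU/mL or more to below LLOQ: at least log10(20,000/15) = 3.12.
- Untreated starting values between the entry limit and the ULOQ of 170,000,000 IU/mL span log10(1.7e8/2e4) = 3.93. If uniform on that range, their SD is 3.93/√12 = 1.13.

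**Coverage under a pooled variance.** With equal groups and variance constant over visits, s_pooled = √[(s₁² + s₂²)/2], and a nominal 80% interval for group g covers 2Φ(1.2816 × s_pooled/s_g) − 1.

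| SD untreated / suppressed | s_pooled | Untreated | Suppressed |
|---|---|---|---|
| 1.0 / 0.2 | 0.721 | 64.5% | 100% |
| 1.0 / 0.54 | 0.804 | 69.7% | 94.4% |
| 1.13 / 0.54 | 0.886 | 68.5% | 96.4% |
| 1.2 / 0.54 | 0.930 | 68.0% | 97.3% |

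Interval width at 1.13 / 0.2 with 12 per group: s_pooled = 0.811, so the common width is 2 × 1.2816 × 0.811/√12 = 0.60 in both groups. Each group's own SD gives 0.84 and 0.15.

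**Variance that changes over visits.** CS also fixes the variance over visits. Two simulations show what follows.

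- Assumed trajectories within the documents' limits, 13 on-treatment visits, 12 per group. With common CS, untreated coverage averages 70%: 74-76% at Week 12 and 56-58% at Week 48. Suppressed coverage is about 95%. Fitting CS by status restores the average to 80% in both groups but leaves untreated coverage at 67-70% at Week 48.
- 26 visits, untreated SD rising linearly from 0.5 at Week 2 to 1.2 at Week 48. The planned model covers 97.5% and 66.7% of the time at those two visits. CS by status and phase covers 96.5% and 64.9%. Small-sample-corrected empirical SEs by visit cover 80.1% and 79.9%.

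**Redundant intercept.** Let J be the all-ones matrix. A random intercept plus CS gives V = (σ_b² + σ_cs)J + σ²I. The derivatives with respect to σ_b² and σ_cs are both J, so three parameters have rank 2 and only the sum is estimable. V itself is unchanged, so LS means and SEs are unaffected.

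**Fallback.** SAP Table 2 has 13 post-baseline on-treatment visits and 13 standard follow-up visits.

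- CS alone: 2 parameters.
- AR(1) alone: 2.
- Toeplitz: one per visit, so 13 on treatment or 26 over both phases.
- Random intercept plus Toeplitz over 13 visits: 14 parameters with rank 13, so the redundancy remains.

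**The case against.** The strongest reply is that intervals based on each group's own SD are already planned. SAP 5.1.6 calls for SD, SE and two-sided 80% CIs on changes from baseline. It also lists, as applicable, the two pooled cohorts that correspond to the model's status groups. That stands. A reader might infer that every status-specific HBV DNA interval, or the error bars in the mean ± SE plots, would be wrong. The documents do not support this: those plots belong to the descriptive analysis, and the pooled variance does not enter them. What remains is that the model's intervals could disagree with the descriptive ones beside them. The SAP 5.1.6 rule does not turn a model with status as a covariate into separate fits.

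The SDs are assumed. The value 0.54 is half of 1.08 and is not a bound. Rises count as well as falls, so the SD could in principle reach 1.08; at 1.13 / 1.08 coverage would be about 79% and 81%. That extreme is unlikely in participants kept on NA, but the size of the error is illustrative.

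A reader might also infer that the untreated interval is too narrow at every visit, or that the finding carries into follow-up. Neither is supported. With growing variance the untreated interval can be too wide early and too narrow late. After NA stops, the protocol (4.2) itself states: "Increases in ALT and HBV DNA are frequently seen in patients after discontinuation of NA treatment". If one of 12 suppressed participants rose from 5 to 100,000 IU/mL and the rest did not change, the SD would be log10(20,000)/√12 = 1.24, enough to close or reverse the gap.

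On the fallback, AR(1) is a reasonable option. It has no more parameters than CS alone, and unlike CS it remains identifiable beside a random intercept. The objection is to Toeplitz and to calling it simpler.

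**Conclusion.** The point holds and is minor. If status-specific LS means are reported for on-treatment HBV DNA, their 80% intervals would be miscalibrated. Under roughly constant variance over visits, equal groups and assumed SDs of 1.0-1.2 (untreated) and 0.2-0.54 (suppressed), coverage is about 64-70% and 94-100%. With variance that changes over visits, the error depends on the visit.

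The claim does not cover status-averaged or between-status intervals, which keep 79-80% coverage with equal groups and constant variance. It also leaves out the descriptive summaries, follow-up after NA stop, HBsAg and HBeAg. Unbalanced follow-up was not simulated.

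Two statements hold whatever the SDs: the random intercept is not identifiable beside CS, and the fallback sentence is wrong as written about Toeplitz. Neither alters an LS mean or SE by itself. The endpoint is secondary, SAP 5.1.7 rules out formal tests, and no decision rule depends on the result.

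**What to change.** 1. Drop the participant random intercept.
2. For HBV DNA, fit the model separately by HBV status (or use GROUP= status) and let the variance differ by visit. Alternatively, keep a simple working CS and base the primary SEs and 80% CIs on small-sample-corrected empirical (sandwich) SEs. One of these should be the primary specification, because CS by status, even when split by phase, does not restore coverage when variance drifts within a phase.
3. Replace the fallback sentence with an ordered list in which no fallback has more parameters than the structure it replaces.
4. State whether the reported LS means are status-specific or averaged over status.

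The cost is SAP wording and a few program options. If the variances are in truth equal, intervals by status are about 1% wider with Satterthwaite df (0.753 against 0.746 log10 at SD 1). With participant-level df of 11 instead of 22 they are about 3% wider (t 1.363 against 1.321). SEs will be slightly less stable with about 9-12 participants per group.

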5.4.2.4.2. HBsAg Thresholds

The number and proportion of participants who meet the following HBsAg thresholds over time will be summarized descriptively.

Thresholds for **HBsAg absolute** values:

- <1000 IU/mL
- <100 IU/mL
- <10 IU/mL
- <1 IU/mL
- <LLOQ (0.05 IU/mL)

Of note, seroclearance of HBsAg is defined as HBsAg <LLOQ.

Thresholds for **HBsAg reduction** from baseline:

- $\geq 0.3 \log_{10}$ IU/mL
- $\geq 0.5 \log_{10}$ IU/mL
- $\geq 1 \log_{10}$ IU/mL
- $\geq 2 \log_{10}$ IU/mL
- $\geq 3 \log_{10}$ IU/mL
- $\geq 4 \log_{10}$ IU/mL

5.4.2.4.3. HBeAg Thresholds

The number and proportion of participants who meet the following HBeAg thresholds over time will be summarized descriptively. The HBeAg thresholds will be summarized only for HBeAg positive participants at study entry.

Thresholds for **HBeAg absolute** values:

- < 100 IU/mL
- < 10 IU/mL
- < 1 IU/mL
- < LLOQ (0.11 IU/mL)

Of note, seroclearance of HBeAg is defined as (quantitative) HBeAg <LLOQ.

Thresholds for **HBeAg reduction** from baseline:

- $\geq 0.3 \log_{10}$ IU/mL
- $\geq 0.5 \log_{10}$ IU/mL
- $\geq 1 \log_{10}$ IU/mL
- $\geq 2 \log_{10}$ IU/mL
- $\geq 3 \log_{10}$ IU/mL

5.4.2.4.4. HBV DNA Thresholds

The number and proportion of participants who meet the following HBV DNA thresholds over time will be summarized descriptively.

Thresholds for **HBV DNA absolute** values:

- < LLOQ
- < LLOQ TND
- < LLOQ TD
- <60 IU/mL
- <100 IU/mL
- <200 IU/mL
- <1000 IU/mL
- <2000 IU/mL
- <20000 IU/mL

Thresholds for **HBV DNA reduction** from baseline:

- $\geq 1 \log_{10}$ IU/mL
- $\geq 2 \log_{10}$ IU/mL
- $\geq 3 \log_{10}$ IU/mL
- $\geq 4 \log_{10}$ IU/mL
- $\geq 5 \log_{10}$ IU/mL

5.4.2.4.5. ALT Decrease and Normalization

A participant with ALT elevation (ALT \geq ULN) at baseline is defined to achieve ALT normalization if his/her ALT value post-baseline is <ULN at any given time point.

The number and proportion of participants who achieve the following ALT normalizations will be summarized descriptively over time, only for the subjects who had ALT elevation at baseline:

- On treatment ALT normalization, i.e., while being treated with JNJ-3989 and/or JNJ-6379 and/or NA and/or PegIFN- α 2a).
- Off treatment ALT normalization, i.e., after stopping JNJ-3989, JNJ-6379, NA, and PegIFN- α 2a.

Descriptive statistics of the absolute values and changes from baseline over time in ALT will be summarized for those participants who had ALT elevation at baseline. An additional summary of descriptive statistics of the ALT absolute values and changes from baseline over time will be provided for participants who had ALT values within the normal range at baseline.

